5.3. Lifestyle Considerations

Throughout the study, participants may undergo medical assessments and review of compliance with requirements before continuing in the study.

5.3.1. Meals and Dietary Restrictions

Participants will receive a light breakfast on the morning of Day 1 prior to dosing. Standard meals will be provided at all other times while participants are resident at the CRU, per the 1 • — (E

5.3.2. Substance Use: Caffeine, Alcohol, and Tobacco

Caffeine

Participants will not be allowed to consume caffeinated products during study visits and while resident at the CRU, but otherwise participants will be allowed to maintain their regular caffeine consumption.

Alcohol

Alcohol consumption is not permitted while participants are resident at the CRU and for 24 hours prior to each study visit. Alcohol intake during outpatient periods should not exceed 3 units per day for males or 2 units per day for females.

Tobacco

Participants must abide by the CRU smoking restrictions during study visits and while resident at the CRU.

5.3.3. Activity

Exercise

Participants will be advised to maintain their regular levels of physical activity or exercise; however, they should not undertake vigorous or prolonged exercise within 48 hours prior to any visit in which laboratory safety tests will occur. While certain study procedures are in progress at the site, participants may be required to remain recumbent or sitting.

Blood or blood products donation

Study participants should be instructed not to donate blood or blood products during the study until the end of study participation.

5.4. Screen Failures

A screen failure occurs when a participant who consents to participate in the clinical study is not subsequently assigned to study intervention.

Rescreening is not permitted. Repeating of laboratory tests during the screening period or repeating screening tests to comply with the protocol-designated screening period does not constitute rescreening.

5.5. Criteria for Temporarily Delaying Randomization of a Participant

Not applicable.

6. Study Interventions and Concomitant Therapy

Study intervention is defined as any medicinal products or medical devices intended to be administered to or used by a study participant according to the study protocol.

6.1. Study Interventions Administered

This table lists the interventions used in this clinical study.

Intervention Name	Lebrikizumab	Placebo
Dosage Formulation	250 mg (125 mg/mL), 2 mL solution for injection in a prefilled syringe with needle safety device	Placebo solution in a prefilled syringe with needle safety device
Dosage Levels	Cohort 1: 250 mg (1 injection of 250 mg) Cohort 2: 500 mg (2 injections of 250 mg)	Not applicable
Route of Administration	Subcutaneous	Subcutaneous
Dosing Instructions	Single dose administration	Single dose administration
Packaging and Labeling	Study interventions will be supplied by the sponsor or its designee in accordance with current Good Manufacturing Practice. Study interventions will be labeled as appropriate for country requirements.	

6.1.1. Administration Details

Lebrikizumab or placebo will be administered by the investigator or designee, using a prefilled syringe with needle safety device. Each prefilled syringe is intended for a single 2 mL dose, 250 mg, administered subcutaneously in the abdomen, thigh, or back of the upper arm.

Whenever possible, study drug administration should be carried out by the same personnel. The location of the injection(s) will be recorded. Multiple injections making up a single dose for Cohort 2 should be apart from each other, so ISRs, if any, can be observed separately.

Administration of placebo will match that for lebrikizumab as either 1 or 2 injections.

Participants may stay in the semi-recumbent position for 2 hours following study drug administration, where possible.

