4.1. Overall Design

This is a Phase 1, participant- and investigator-blinded, randomized, placebo-controlled, single-dose study to investigate the safety, tolerability, and PK of lebrikizumab in healthy Chinese participants.

Approximately 24 healthy Chinese participants who have satisfied the entry criteria and completed all screening assessments will be enrolled to ensure at least 20 evaluable participants complete the study. Due to effect of body weight on PK, enrolment of participants with similar body weights between the cohorts is preferred. Participants will be assigned sequentially into 1 of 2 cohorts, each with 12 participants. Within each cohort, participants will be randomized in a blinded manner to lebrikizumab or placebo. The planned doses are as follows:

- Cohort 1: single 250 mg dose of lebrikizumab or placebo via SC injection (n=12; 10 lebrikizumab, 2 placebo)
- Cohort 2: single 500 mg dose of lebrikizumab or placebo via SC injection (n=12; 10 lebrikizumab, 2 placebo)

The duration of the study is approximately 21 weeks, and will consist of 3 periods:

- Screening period: Day -28 to Day -2
- Inpatient period: Day -1 to Day 8
 - single SC dose on Day 1
- Follow-up period: discharge until Day 120 ± 3 days.

Screening period

All participants will be screened within 28 days prior to enrollment.

Inpatient period

Eligible participants will be admitted to the CRU on Day -1. On Day 1, participants will be randomized, and will receive either lebrikizumab or placebo via SC injection.

Participants may be allowed to leave the CRU after completing assessments on Day 8, or later at the investigator's discretion.

Follow-up period

Participants will return for PK and immunogenicity sampling and safety assessments at predefined times up to approximately 120 days postdose.

Safety and tolerability will be assessed through safety laboratory assessments, 12-lead ECGs, vital sign measurements, recording of AEs, and physical examinations.

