9.5. Sample Size Determination

Approximately 24 participants will be enrolled in 2 dosing cohorts for at least 20 evaluable participants to complete the study. The sample sizes described are customary for Phase 1 studies evaluating safety and PK parameters and are not powered on the basis of statistical hypothesis testing. Each cohort will comprise approximately 12 participants with a randomization ratio of 5:1 between lebrikizumab and placebo. Participants who discontinue the study before completing may be replaced at the discretion of the sponsor and investigator. The replacement participant can complete the entire study period.

10. Supporting Documentation and Operational Considerations

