6. STUDY TREATMENTS

The study treatment names, and ordering to be used in the TFLs are presented in [Table 1](#).

Table 1: Presentation of Study Treatments in TFLs

Study Treatment	Order in TFLs
Placebo SC	1
250 mg lebrikizumab SC	2
500 mg lebrikizumab SC	3

Abbreviations: SC = subcutaneous

All TFLs will be based on actual treatments.

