8.6.5. Injection-Site Reactions and Visual Analog Scale Pain Scores

ISR data (erythema, induration, categorical pain, pruritus, and edema) will be listed and, if there are sufficient data, summarized by treatment in frequency tables.

In addition, if injection-site pain is reported, the intensity of pain will be quantified using the 100-mm validated pain VAS. All data will be listed.

The pain categories of VAS for presentation in the TFLs will be no pain (VAS pain score = 0), mild pain (VAS pain score > 0 and ≤ 30), moderate pain (VAS pain score > 30 and ≤ 70), and severe pain (VAS pain score > 70).

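### Injection number is confounded with dose, and the planned injection-site reaction tables have no per-injection denominator and no placebo column matched on injection number

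*Protocol*

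**What the plan says.** Protocol 6.1 gives 250 mg as one prefilled syringe and 500 mg as two. Under 6.1.1 each syringe holds 2 mL containing 250 mg, and for placebo: "Administration of placebo will match that for lebrikizumab as either 1 or 2 injections". Injection location is recorded, and for the two-injection cohort the protocol adds: "Multiple injections making up a single dose for Cohort 2 should be apart from each other, so ISRs, if any, can be observed separately".

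On allocation, Protocol 9.5 states: "Each cohort will comprise approximately 12 participants with a randomization ratio of 5:1 between lebrikizumab and placebo". Section 4.1 gives this as 10 lebrikizumab and 2 placebo in each cohort.

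SAP section 6 sets the display groups: "The study treatment names, and ordering to be used in the TFLs are presented in" Table 1. That table has three rows: one placebo group, 250 mg and 500 mg. SAP 8.6.5 lists the ISR data and, "if there are sufficient data, summarized by treatment in frequency tables". Section 8.6.6 repeats this. Neither section says whether the tables count participants, injections or reactions.

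SAP 8.6.1 plans both participants and number of events for treatment-emergent adverse events (TEAEs) overall and by severity. The tables by system organ class and preferred term count participants only. ISRs are an adverse event of special interest (AESI) in Protocol 8.3.3 and SAP 8.6.1. Protocol 8.2.6.2 records each reported ISR as an adverse event, so ISRs also enter the primary endpoint.

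**The concern.** Every 250 mg participant has one opportunity for a local reaction and every 500 mg participant has two. Injection number is therefore fully confounded with dose. The design contains a matched control for this, because each cohort's placebo participants receive the same number of injections as its active participants. Pooling them into one column removes the match: the column averages 1.5 injections per participant, more than 250 mg and fewer than 500 mg.

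The protocol keeps the sites apart and records their location, but no planned summary uses that information. In a descriptive study with safety as the primary objective, the tables are the result. A gradient from placebo or 250 mg up to 500 mg could be read as a dose effect on local tolerability when it reflects the number of needles.

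**Working it through.** **Inputs from the documents.** Twelve participants per cohort at 5:1; one injection per dose in Cohort 1 and two in Cohort 2, active and placebo alike (Protocol 4.1, 6.1, 6.1.1, 9.5).

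**Allocation reproduced.** 12 × 5/6 = 10 lebrikizumab and 12 × 1/6 = 2 placebo per cohort; 2 × 12 = 24 in total. This agrees with the protocol.

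**Planned injections.** 250 mg: 10 × 1 = 10. 500 mg: 10 × 2 = 20. Placebo: 2 × 1 + 2 × 2 = 6. Total 36.

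**Assumptions.** The documents give neither an ISR risk per injection, p, nor a correlation, ρ, between two injections in the same person. Both are varied below. Risk per injection is set equal in all groups, so there is no drug or dose effect. For the two active doses this is a natural reference case, since each syringe delivers the same 250 mg in 2 mL.

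**Formulas for the share of participants with at least one ISR.**
- One injection: p
- Two injections: q = 1 − [(1 − p)² + ρp(1 − p)]
- Pooled placebo: (2p + 2q)/4

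With p = 0.10 and ρ = 0, q = 1 − 0.81 = 0.19 and pooled placebo is (0.20 + 0.38)/4 = 0.145. With ρ = 0.5, q = 1 − (0.81 + 0.045) = 0.145.

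| p | ρ | 250 mg | 500 mg | Ratio | Pooled placebo |
|---|---|---|---|---|---|
| 0.05 | 0 | 5.0% | 9.75% | 1.95 | 7.4% |
| 0.10 | 0 | 10.0% | 19.0% | 1.90 | 14.5% |
| 0.10 | 0.5 | 10.0% | 14.5% | 1.45 | 12.25% |
| 0.10 | 1 | 10.0% | 10.0% | 1.00 | 10.0% |
| 0.30 | 0 | 30.0% | 51.0% | 1.70 | 40.5% |
| 0.30 | 0.5 | 30.0% | 40.5% | 1.35 | 35.25% |

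At p = 0.10 and ρ = 0, pooled placebo lies 4.5 points above 250 mg and 4.5 points below 500 mg, although nothing differs except injection number.

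**If reactions are counted instead of participants.** At p = 0.10 the expected counts are 10 × 0.10 = 1 at 250 mg and 20 × 0.10 = 2 at 500 mg. The doubling holds whatever the correlation.

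**How often the gap would appear.** Taking the two arms as independent binomials, 10 participants each, with probabilities p and q:

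| p | ρ | 500 mg higher | Tie | 250 mg higher |
|---|---|---|---|---|
| 0.05 | 0 | 0.47 | 0.35 | 0.18 |
| 0.10 | 0 | 0.60 | 0.22 | 0.18 |
| 0.10 | 0.5 | 0.48 | 0.27 | 0.25 |
| 0.30 | 0 | 0.77 | 0.11 | 0.11 |

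At p = 0.10 with independence, a tie or reversal has probability 0.22 + 0.18 = 0.40.

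**With a per-injection denominator.** The expected rate is p in every group, for any ρ, so the artificial gap is zero in expectation.

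**The case against.** The strongest reply is that two injections are how 500 mg is given here. The objective is to describe the safety of single 250 mg and 500 mg doses, so the local burden of the second injection belongs in that description. There is no hypothesis test, and no planned text attributes an ISR difference to drug or dose. This stands: the participant-level table is valid and should stay.

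The placebo mismatch is also small against the noise. At 10% risk it is 4.5 points, while one participant among four is 25 points. A split leaves two participants in each part. With no events, the exact two-sided 95% upper limits are 1 − 0.025^(1/2) = 84% for two injections and 1 − 0.025^(1/4) = 60% for four, even treating injections as independent. This also stands: a separate placebo column would add little beyond a flag.

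Three stronger readings are tempting, and the documents do not support them.

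- *A reader might infer that ISRs are summarised only per participant.* SAP 8.6.5 and 8.6.6 state no unit, and SAP 8.6.1 plans event counts for TEAEs overall and by severity. Those event counts do not isolate ISRs, however, and the accompanying table shells, which might settle the unit, are not among the documents.
- *A reader might infer that 500 mg will look worse.* It is expected to, under the stated assumptions, but within-person correlation shrinks the participant-level gap and chance often hides it.
- *A reader might infer that injection number and dose can never be separated, or that the ISR form lacks a link to the site.* SAP 8.1 lists all captured data and injection location is recorded, so a per-injection count may be recoverable by hand. Protocol 8.2.6.2 describes the ISR form only by example, so a missing link is not shown.

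**Conclusion.** The point holds as a minor matter of presentation and interpretation. Injection number is fully confounded with dose, the counting unit of the ISR tables is unstated, no per-injection denominator is planned, and the single placebo column matches neither dose.

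For independent reactions and per-injection risks of 5% to 30%, the expected 500 mg to 250 mg ratio of affected participants is 1.95 to 1.70 with no true effect. At 10% risk it falls to 1.45 at correlation 0.5 and to 1 at correlation 1. These figures rest on assumed risks and correlations and on equal risk per injection in all groups. No error rate or decision rule is affected. What is exposed is the reading of an apparent dose gradient in an AESI.

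**What to change.** In SAP 8.6.5 and 8.6.6:

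1. State the counting unit of the ISR frequency tables and keep the participant-level table.
2. Add a supplementary display of injections with a reaction over injections given, by treatment, with planned denominators 10, 20 and 6. Keep it descriptive: the 20 injections at 500 mg come from 10 people and should not be treated as 20 independent observations.
3. Flag placebo ISRs as following one or two injections, in the table or the listing. The n < 3 rule in SAP 8.1.1 applies to continuous summaries, so it does not prevent showing these counts.
4. Confirm before the first participant is dosed that the ISR data identify the injection site of each reaction, since this may not be recoverable afterwards.

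The cost is a few lines of SAP text, one extra table and one check of the ISR form. The downside is sparse placebo cells (2 and 4 injections), which can be shown as counts but support no comparison on their own.

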6.2. Preparation, Handling, Storage, and Accountability

The investigator or designee must confirm appropriate storage conditions have been maintained during transit for all study intervention received and any discrepancies are reported and resolved before use of the study intervention.

Only participants enrolled in the study may receive study intervention. Only authorized study personnel may supply, prepare, or administer study intervention.

All study intervention must be stored in a secure, environmentally controlled, and monitored, manual or automated, area in accordance with the labeled storage conditions with access limited to the investigator and authorized study personnel.

The investigator or authorized study personnel are responsible for study intervention accountability, reconciliation, and record maintenance, that is, receipt, reconciliation, and final disposition records.

Further guidance and information for the final disposition of unused study interventions are provided in the pharmacy manual.

Note: In some cases, sites may destroy the material if, during the investigative site selection, the evaluator has verified and documented that the site has appropriate facilities and written procedures to dispose of clinical materials.

6.3. Assignment to Study Intervention

6.4. Blinding

This is a participant- and investigator-blind study. The sponsor will not be blinded to treatment assignment; however, to preserve the blinding of the study, a minimum number of Lilly personnel and staff at the CRU, namely, CRU pharmacy staff, will see the randomization table before the study is complete. Individuals involved in the blinding of the study intervention will not be involved in any of the clinical aspects of the study, including study intervention administration and AE assessments.

Participants will be randomly assigned in a 5:1 ratio to receive lebrikizumab and placebo. All study site personnel, except staff who prepare or dispense study medication, will remain blinded.

To maintain this blind, an otherwise uninvolved third party, unblinded site or CRU pharmacy staff, will be responsible for the removal of the tear-off portion of the label and dispensation of all study intervention and will endeavor to ensure that there are no differences in time taken to dispense following randomization.

In the event of a quality assurance audit, the auditor will be allowed access to unblinded study intervention records at the site to verify that randomization or dispensing has been done accurately.

Emergency codes will be available to the investigator. A code, which reveals the study intervention for a specific study participant, may be opened during the study only if the

In case of an emergency, the investigator has the sole responsibility for determining if unblinding

Where feasible and when timing of the emergent situation permits, the investigator should

assignment. If the investigator decides that unblinding is warranted, it is the responsibility of the investigator to promptly document the decision and rationale and notify Lilly as soon as possible.

Upon completion of the study, all codes must be returned to Lilly or its designee.

If an investigator, site personnel performing assessments, or participant is unblinded, the participant must be discontinued from the study. In cases where there are ethical reasons to have the participant remain in the study, the investigator must obtain specific approval from a sponsor clinical research physician or clinical pharmacologist for the participant to continue in the study.

6.5. Study Intervention Compliance

Study intervention will be administered under medical supervision by the investigator or designee. The dose of study intervention and study participant identification will be confirmed prior to the time of dosing. The date and time of each dose administered will be recorded in the source documents and will be provided to the sponsor as requested.

6.6. Dose Modification

Dose adjustments are not permitted in this study.

6.7. Continued Access to Study Intervention after the End of the Study

Study intervention will not be made available after conclusion of the study to participants.

6.8. Treatment of Overdose

For this study, any dose of study intervention greater than the dose of study intervention assigned through randomization will be considered an overdose.

The sponsor does not recommend specific treatment for an overdose.

In the event of an overdose, the investigator should

contact the medical monitor immediately

evaluate the participant to determine, in consultation with the medical monitor, whether study intervention should be interrupted or whether the dose should be reduced

closely monitor the participant for any AE or SAE and laboratory abnormalities as medically appropriate, and

obtain a blood sample for PK analysis if requested by the medical monitor, determined on a case-by-case basis.

6.9. Prior and Concomitant Therapy

Any medication or vaccine, including over-the-counter or prescription medicines, vitamins, or herbal supplements, or other specific categories of interest that the participant is receiving at the time of enrollment or receives during the study must be recorded along with the

reason for use

dates of administration including start and end dates, and

dosage information including dose and frequency for concomitant therapy of special interest.

The medical monitor should be contacted if there are any questions regarding concomitant or prior therapy.

Participants must abstain from taking over-the-counter, prescription medication including herbal medications and traditional Chinese medicines within 7 days, or 14 days if the drug is a potential enzyme inducer, or 5 half-lives, whichever is longer, prior to dosing and throughout the study. In addition, prior to dosing, the participant must also abstain from taking

biologic agents, such as monoclonal antibodies, including marketed drugs, within 3 months or 5 half-lives, whichever is longer, and

live vaccines, including attenuated live vaccines, within 12 weeks prior to screening.

Stable doses of hormone contraceptives, hormone-replacement therapy or thyroid replacement are permitted, at the discretion of the investigator. Supplements, for example vitamin supplements, may be permitted at the discretion of the investigator.

Acetaminophen, at doses of less than or equal to 2 grams/day, is permitted for use any time during the study. Other concomitant medication may be considered on a case-by-case basis by the investigator in consultation with the medical monitor, if required.

7. Discontinuation of Study Intervention and Participant Discontinuation/Withdrawal

Discontinuation of specific sites or of the study as a whole are handled as part of Section 10.

7.1. Discontinuation of Study Intervention

Not applicable.

7.2. Participant Discontinuation/Withdrawal from the Study

Discontinuation is expected to be uncommon.

A participant may withdraw from the study

- at any time at () own request for any reason or without providing any reason
- at the request of () designee, for example, parents or legal guardian
- at the discretion of the investigator for safety, behavioral, compliance, or administrative reasons, or
- if enrolled in any other clinical study involving an investigational product, or enrolled in any other type of medical research judged not to be scientifically or medically compatible with this study.

At the time of discontinuing from the study, if possible, the participant will complete procedures for an early discontinuation visit, as shown in the SoA in Section 1.3.

If the participant withdraws consent for disclosure of future information, the sponsor may retain and continue to use any data collected before such a withdrawal of consent. If a participant withdraws from the study, the participant may request destruction of any samples taken and not tested, and the investigator must document this in the site study records.

